8.2.2 Intensity

The intensity of an AE will be graded according to the following definitions:

- Grade 1: Mild; the participant experiences awareness of signs or symptoms but these are easily tolerated or managed without specific treatment
- Grade 2: Moderate; the participant experiences discomfort enough to cause interference with usual activity, and/or the condition requires specific treatment
- Grade 3: Severe; the participant is incapacitated with inability to work or do usual activity, and/or the event requires significant treatment measures
- Grade 4: Disabling or with life threatening consequences, urgent intervention indicated
- Grade 5: Death

CONFIDENTIAL

8.2.3 Relationship to Study Product

The relationship of an AE to the study product should be determined by the investigator according to the following criteria:

- Not related: The event is most likely produced by other factors such as the participant's clinical condition, intercurrent illness, or concomitant drugs, and does not follow a known response pattern to the study product, or the temporal relationship of the event to study product administration makes a causal relationship unlikely
- Unlikely related: The event is most likely produced by other factors such as the participant's clinical condition, therapeutic interventions, or concomitant drugs administered to the participant and it does not follow a known response pattern to the study product
- Possibly related: The event follows a reasonable temporal sequence from the time of study product administration, and/or follows a known response pattern to the study product, but could have been produced by other factors such as the participant's clinical condition, intercurrent illness, or concomitant drugs
- Related: The event follows a reasonable temporal sequence from the time of study product administration, and/or follows a known response pattern to the study product, and cannot be reasonably explained by other factors such as the participant's clinical condition, intercurrent illness, or concomitant drugs

8.3 Discontinuation due to Adverse Events

Any participant who experiences an AE may be withdrawn at any time from the study at the discretion of the investigator. Participants withdrawn from the study due to an AE, whether serious or nonserious, may be followed by the investigator until the clinical outcome of the AE is determined. The AE(s) should be noted on the appropriate eCRFs and the participant's progress should be followed until the AE is resolved or stabilized as determined by the investigator. The sponsor and medical monitor must be notified. If the AE relates to overdose of study treatment, the Investigator's Brochure should be consulted for details of any specific actions to be taken.

8.4 Reporting Serious Adverse Events

Serious adverse events will be collected beginning at ICF signing and in an ongoing manner through the follow-up telephone call. In the event of any SAE reported or observed during the study, whether or not attributable to the study product, site personnel will report it immediately by telephone to the sponsor, medical monitor, and SAE hotline at ICON (ICON plc Pharmacovigilance) in accordance with procedures described in the SRM and/or SAE study-specific procedure. Site personnel will follow up with a written report to the sponsor on the next working day.

SAE Report Forms will be provided to the CRU to assist in collecting, organizing, and reporting SAEs and follow-up information.

CONFIDENTIAL

All SAEs should be followed to their resolution, with documentation provided to the sponsor, medical monitor, and ICON on a follow-up SAE Report Form.

CONFIDENTIAL

9 STATISTICAL CONSIDERATIONS

The statistical analysis will be conducted following the principles as specified in ICH Topic E9 (CPMP/ICH/363/96).

All statistical analyses will be described in a separate statistical analysis plan.

9.1 Sample Size Calculation

A total of 20 healthy, postmenopausal female participants (N = 10 per arm) are planned for inclusion in this study. The sample size for this study is based on the desire to accurately assess the safety, tolerability, and PK of the DARE-HRT1 IVR over a 12-week period. The sample sizes provided are deemed sufficient to allow for adequate assessment of the IVR. Dropouts may be replaced. Participants who terminate early from the trial may be replaced to ensure an adequate number of participants contributing safety data from extended treatment with the IVR for each treatment arm.

9.2 Analysis Populations

Safety Population: all enrolled participants who received active treatment, i.e., inserted an IVR (and thus who were exposed to one of the IVRs).

All safety analyses (primary endpoints) will be conducted in the Safety Population.

Pharmacokinetic Population: all participants who received a full course of study treatment for their dispensed treatment and who have sufficient concentration data for determination of PK parameters (primary endpoint); data will be analyzed according to the actual study treatment received.

All PK analyses will be conducted in the Pharmacokinetic Population.

Modified Intent-to-treat (mITT) Population: all enrolled participants who received active treatment and who underwent a baseline assessment and at least 1 post-treatment assessment of at least 1 of the following exploratory assessments: Usability and Tolerability questionnaire, vaginal cytology, vaginal pH, most bothersome symptom, or VMS (MENQOL)

All exploratory analyses will be conducted in the mITT population.

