Endometrial biopsy ^d	X ^e															
Height (cm), weight (kg), and BMI ^f	X	X			X					X			X			
12-lead ECG	X															
Vital signs (BP and PR), RR, oral temperature	X	X		X	X		X	X	X	X		X	X			
Hematology and blood chemistry	X	X		X	X		X	X	X	X		X	X			
Urine dipstick	X	X			X					X			X			
FSH	X															

CONFIDENTIAL

Study Procedure	Screening	Cycle 1			Cycle 2					Cycle 3			EOS / ET		Follow-Up Phone Call
		Days -28 to -2	1	2, 3	8, 15, 22	1	2, 3	8	15	22	1	2, 3	8, 15, 22	29	
Serology tests ^g	X														
Drug and alcohol urine screen	X	X													
Training on use of IVR	X	X													
Randomization		X ^h													
Dispense IVR(s)		X			X					X					
Insert new IVR (after predose PK sample) ⁱ		X			X					X					
Remove used vaginal ring/return IVR(s)					X					X			X		
Confirm IVR placement		X ^j	X	X	X ^j	X	X	X	X	X ^j	X	X			
PK blood samples ^k	X	X ^l	X	X	X ^l	X	X	X	X	X ^l	X	X	X ^m	X ^m	
Usability and Tolerability questionnaire					X					X			X		
Vulvovaginal atrophy symptoms including most bothersome symptom		X											X		
MENQOL questionnaire		X											X		
Dispensing / Review of daily diary	X				X					X			X		
Adverse events, including serious adverse events	Adverse events and serious adverse events collected beginning at ICF signing and in an ongoing manner														
TEAEs	TEAEs collected beginning at IVR placement and in an ongoing manner as appropriate														
Prior/concomitant medications	X	Concomitant medications collected in ongoing manner, as appropriate													
Follow-up telephone call ^a															X

Abbreviations: AE = adverse event; BMI = body mass index; BP = blood pressure; ECG = electrocardiogram; EOS = end of study; ET = early termination; FSH = follicle-stimulating hormone; HCV = hepatitis C virus; HIV = human immunodeficiency virus; ICF = informed consent form; ID = identification;

CONFIDENTIAL

IVR = intravaginal ring; MENQOL = Menopause-specific Quality of Life; PK = pharmacokinetic; PR = pulse rate; RR = respiratory rate; SAE = serious adverse event; TEAE = treatment-emergent adverse events; temp = temperature.

- a. Participants undergoing washout of prior hormone replacement therapy will be required to sign the ICF before starting washout. Where washout of HRT will take approximately 8 weeks, screening procedures should not commence until 28 days prior to Cycle 1, Day 1.

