include any active hormone components. In addition to evaluating participants' comprehension of the instructions for use, participants were also evaluated on their ability to properly insert and remove the rings and were asked to report on the acceptability and tolerability of the IVR. The study demonstrated that the placebo IVRs were safe and well tolerated, in terms of reported adverse events (AEs) and physicians' assessments and evaluation of the vaginal mucosa, vaginal sections, epithelial integrity, epithelial surface thickness, and vaginal color. The most frequently reported AE was vulvovaginal discomfort in 8 of 44 (18.2%) treated participants. Subjects generally found the instructions provided for the IVR easy to understand, and 32 of 44 (73.7%) participants were able to successfully insert and remove the IVR. The IVRs were reported to be comfortable by the majority of participants, with most participants reporting that the IVR was convenient to use and worked with their lifestyle.

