6.2 Treatments Administered

Each participant will be assigned to receive an IVR (Dose 1 or Dose 2) for 12 weeks, across three 28-day cycles, with a new IVR administered on Day 1 of each cycle. In Cycles 2 and 3, the new IVR should be self-administered as soon as possible after the previous IVR has been removed.

For each cycle, Day 1 is defined as the first day of treatment, i.e., the day the IVR is self-administered by the participant. Correct placement of the IVR will be confirmed by the study staff. The same IVR is to remain in position for 28 days, with removal of the IVR by the participant in the CRU on the morning of Day 1 of the next cycle.

If a participant cannot self-insert the IVR, the site physician will insert the IVR.

At the end of each cycle, participants will remove their own IVR.

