7.7 Safety Assessments

7.7.1 Adverse Events

Participants will be monitored for AEs from the time of consent. Treatment-emergent AEs (TEAEs) will be those with an onset after insertion of the first IVR through the follow-up telephone call. Serious adverse events will be collected beginning at ICF signing and in an ongoing manner through the follow-up telephone call. Refer to Section 8 for additional details.

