8 ADVERSE EVENTS

An AE is defined as any untoward medical occurrence in a participant administered a pharmaceutical product during the course of a clinical investigation. An AE can therefore be any unfavorable and unintended sign, symptom, or disease temporally associated with the use of a study drug/product, whether or not thought to be related to the study drug/product.

Participants will be monitored for AEs throughout the study from the time of consent. Treatment-emergent AEs (TEAEs) will be those with an onset after insertion of the first IVR through the follow-up telephone call. Adverse events that are identified at the last assessment visit (or the early termination visit) as specified in the protocol must be recorded on the AE eCRF with the status of the AE noted. All events that are ongoing at this time will be recorded as ongoing on the eCRF. All (both serious and nonserious) AEs must be followed until they are resolved or stabilized, or until reasonable attempts to determine resolution of the event are exhausted. The investigator should use his/her discretion in ordering additional tests as necessary to monitor the resolution of such events.

The procedures specified in Section 8.4 are to be followed for reporting SAEs.

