9.4 Endpoints

9.4.1 Primary Endpoints

The primary endpoints are as follows:

- Incidence and severity of AEs
- Changes from baseline in clinical laboratory findings
- Changes from baseline in physical examination findings
- Changes from baseline in vital signs results
- Changes from baseline in speculum examination findings
- Changes from baseline in transvaginal ultrasound findings
- Steady-state concentration (C_{ss}) and maximum observed plasma concentration (C_{max}) in each cycle for estradiol, estrone, and progesterone

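### The Safety Population and the TEAE window both start at ring insertion, so a failed first insertion drops the woman from the primary safety analyses, and an event that begins during an eventually successful attempt misses the TEAE tables

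*Combined protocol and SAP*

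**What the plan says.** Section 9.2 defines the Safety Population as "all enrolled participants who received active treatment, i.e., inserted an IVR (and thus who were exposed to one of the IVRs"). It then states: "All safety analyses (primary endpoints) will be conducted in the Safety Population".

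Section 7.7.1, repeated in section 8, says that TEAEs "will be those with an onset after insertion of the first IVR through the follow-up telephone call". The schedule of events (Table 1-1) words the start slightly differently: "TEAEs collected beginning at IVR placement and in an ongoing manner as appropriate".

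Adverse events as such are collected earlier. Section 8 says: "Participants will be monitored for AEs throughout the study from the time of consent". The primary endpoint in section 9.4.1 is "Incidence and severity of AEs", without restriction to TEAEs. Section 9.6 promises a descriptive summary or tabulation of adverse events, but the only incidence table it specifies (by system organ class and preferred term) is for TEAEs, and so is the classification by severity and relationship.

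Randomisation comes before treatment starts (section 9.3). On a failed self-insertion, section 6.2 says: "If a participant cannot self-insert the IVR, the site physician will insert the IVR". The protocol does not say how a woman is to be analysed if that attempt also fails, or if she declines it. Sections 5.4 and 9.1 allow women who leave early to be replaced.

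**The concern.** With a vaginal ring, contact with the product begins when someone tries to insert it. Pain, abrasion or bleeding from the attempt is a tolerability finding, and tolerability is part of a primary objective. The setting makes this more than a formality. Section 2.1 describes thinner epithelium and reduced elasticity and lubrication after oestrogen loss. Section 2.3 gives vulvovaginal discomfort as the commonest adverse event with the placebo ring (8 of 44). Section 2.3.1.2 notes that the previous study did not separate ring-related from drug-related events.

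Both the population and the TEAE window are defined by completed insertion. A woman who cannot tolerate the first insertion is removed for a reason tied to how the product performs. The exclusion works in the product's favour and comes after randomisation. In arms of 10, one woman is visible in the percentages.

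**Working it through.** **Definitions, case by case.** The plan states no power or precision calculation that bears on this, so the main check is to apply the rules to each outcome of the first insertion.

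1. *Self-insertion succeeds without trouble.* The woman is in the Safety Population and later events are TEAEs. There is no gap.
2. *An attempt causes pain or injury, and the ring is then placed by her or by the physician.* She has been exposed to a ring and is in the Safety Population, although 9.2 does not say who must have inserted it. The event began before insertion. It is an adverse event, because collection starts at consent, and it falls within the primary endpoint as worded. It fails the TEAE definition, so it is absent from the incidence table and the severity and relationship classification of section 9.6.
3. *Insertion is attempted and no ring is ever placed.* She is outside the Safety Population. She is also outside the PK Population, which needs a full course of treatment, and the mITT Population, which needs active treatment. Her event goes on the eCRF but does not enter the primary safety analyses.
4. *Difficulty occurs at the Cycle 2 or Cycle 3 change.* A first ring has already been inserted, so the event is inside the TEAE window. There is no gap.

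The gap is therefore confined to Cycle 1 Day 1: complete for case 3, limited to the TEAE tables for case 2.

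**Size of one case 3 exclusion.** The input is 10 women per arm (section 9.1). Suppose one woman has an event from the attempt and no ring is placed. Intervals are exact (Clopper-Pearson) 95%.

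| Situation in her arm | As written | Attempt-based definitions |
|---|---|---|
| No other woman has an event | 0/9 = 0% (0 to 33.6%) | 1/10 = 10% (0.3 to 44.5%) |
| Two other women have an event | 2/9 = 22.2% | 3/10 = 30.0% |
| No other event, and she is replaced | 0/10 = 0% (upper limit about 31%) | 1/11 = 9.1% (0.2 to 41.3%) |

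**How likely is at least one such woman?** The documents give no rate of complete insertion failure, so the rate *p* is an assumption. With 20 women, the chance of at least one is 1 − (1 − *p*)^20:

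- *p* = 1%: 1 − 0.99^20 = 18%
- *p* = 2%: 1 − 0.98^20 = 33%
- *p* = 5%: 1 − 0.95^20 = 64%

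These show only how the chance varies with the assumed rate.

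**The case against.** The strongest reply is that the plan loses less than it seems to. Adverse events are collected from consent, the primary endpoint is worded as adverse events, and section 9.6 opens with a summary of adverse events for each participant. A reader might infer that any injury from a first attempt disappears from the primary safety analysis. The documents do not support that where a ring is later placed: the woman is analysed and her event counts as an adverse event. What she loses is its place in the TEAE tables. This part of the objection stands and sets the scope of the point.

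A reader might also infer that the information cannot be recovered from any other output. That cannot be shown. Section 9 defers the analyses to a separate SAP whose text is not available, and disposition tables or listings of pre-treatment events may be planned there.

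A third tempting step is to take a failure rate from the human factors study, in which 32 of 44 "participants were able to successfully insert and remove the IVR". The other 12 did not manage both insertion and removal on their own. That says nothing about failure after a physician has also tried, which is the main route out of the Safety Population, so the figure is not used here. Nor does the previous Phase 1 study give a rate: 34 women were randomised and 33 treated, but neither the arm nor the reason is stated for the remaining one.

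The design also makes complete failure less likely: screening includes a speculum and bimanual examination, participants are trained before use, and the physician is a back-up. Finally, an exposure-based safety set is a coherent choice, and the protocol does not define insertion as completed placement. A site could treat a partly inserted ring as exposure. That ambiguity is itself a reason to settle the wording. None of this covers the woman in whom no ring is placed.

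**Conclusion.** The point holds in a limited form. As worded, a randomised woman with an attempted but never completed first insertion is outside the Safety Population, and neither she nor an event from the attempt enters the primary safety analyses. In a woman whose ring is eventually placed, an event that starts during the attempt is an adverse event but not a TEAE, and is missing from the incidence, severity and relationship tables specified for TEAEs.

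The effect is one woman, or 10% of an arm, each time the first case occurs; its direction favours the product. The case is probably uncommon, its frequency cannot be estimated from the documents, and the unseen SAP may already deal with part of it. The conclusion assumes that inserted means placed; on a looser reading some partial insertions would already count. In a small, largely descriptive study with no formal hypothesis this is a minor point, worth making because it is cheap to correct.

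**What to change.** - **Section 9.2:** define the Safety Population as all randomised participants in whom insertion of an IVR was attempted, by the participant or by the physician.
- **Sections 7.7.1 and 8, and Table 1-1:** define TEAEs as events with onset from the start of the first insertion attempt, leave the end of the window as it is, and use the same wording in all three places.
- **Day 1 eCRF page:** add the time of the first attempt and its outcome.
- **Reporting:** give the number of failed first insertions by arm, counting women who were later replaced.
- **SAP:** carry over the same definitions.

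The cost is a few lines of text and two eCRF fields. No clinical procedure changes. The downside is that the reported TEAE rate may be slightly higher.

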9.3 Randomization

Upon completion of their screening procedures and confirmation of their eligibility (including a transvaginal ultrasound and, if needed, an endometrial biopsy and/or cervical screening test), eligible participants will return to the CRU on Cycle 1 Day 1 and will be randomized.

Randomization will occur prior to initiation of treatment. Participants will be randomized in a 1:1 ratio to the two treatment groups.

CONFIDENTIAL

9.4 Endpoints

9.4.1 Primary Endpoints

The primary endpoints are as follows:

- Incidence and severity of AEs
- Changes from baseline in clinical laboratory findings
- Changes from baseline in physical examination findings
- Changes from baseline in vital signs results
- Changes from baseline in speculum examination findings
- Changes from baseline in transvaginal ultrasound findings
- Steady-state concentration (C_{ss}) and maximum observed plasma concentration (C_{max}) in each cycle for estradiol, estrone, and progesterone

9.4.2 Exploratory Endpoints

Exploratory endpoints are as follows:

- Responses to the Usability and Tolerability questionnaire
- Change from baseline to Week 12 in responses to the MENQOL questionnaire
- Mean change from baseline to Week 12 in the severity of the participant's VVA signs and symptoms
- Mean change from baseline to Week 12 in the severity of the participant's most bothersome VVA symptom
- Mean change from baseline to Week 12 in vaginal pH
- Mean change from baseline to Week 12 in vaginal maturation index (parabasal, intermediate, and superficial cells)

9.5 Pharmacokinetic Statistical Analysis

The PK analysis will be performed for each IVR dose. Graphics will be provided to allow for visual inspection of the mean and individual participant concentration-time profiles.

The PK parameters C_{ss} , C_{max} , t_{max} , and AUC_{D1-D29} will be determined from the plasma concentration-time profiles, where possible. Geometric mean values and coefficients of variation (CV%) will be estimated and reported.

If possible, the dose proportionality for the DARE-HRT1 IVR estradiol and progesterone doses will be assessed.

Other details of the PK analysis will be described in a separate statistical analysis plan.

CONFIDENTIAL

9.6 Safety Analysis

Adverse events, concomitant medications, clinical laboratory findings, physical examinations, speculum examination findings, transvaginal ultrasound results (and endometrial biopsy findings if required), and vital signs for each participant will be tabulated or summarized descriptively, where appropriate.

Vital signs data (observed and change from baseline) will be summarized by time point and treatment using appropriate descriptive statistics. Using the safety population, changes from baseline at each post-randomization visit and end of treatment will be compared between treatment arms. Qualitative analysis of laboratory tests in terms of abnormality will be performed. Findings on physical examination at screening and end of treatment will be reported and compared.

The number and percentage of participants reporting any TEAE will be tabulated by system organ class and preferred term for each treatment (coded using Medical Dictionary for Regulatory Activities [MedDRA] version 24.1 or later). All TEAEs will be further classified by severity and relationship to treatment.

CONFIDENTIAL

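### A between-arm comparison of vital-sign changes is planned at 10 women per arm with no stated adjustment for the baseline value

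*Combined protocol and SAP*

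**What the plan says.** Section 9.4.1 lists "Changes from baseline in vital signs results" among the primary endpoints. Section 9.6 first promises description: "Vital signs data (observed and change from baseline) will be summarized by time point and treatment using appropriate descriptive statistics". The next sentence goes further and says that, in the safety population, "changes from baseline at each post-randomization visit and end of treatment will be compared between treatment arms". That sentence does not repeat the name of the measure, but it follows directly on the vital-sign sentence and is read that way here. It gives no test, model, covariate, estimate or interval.

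On size, Section 9.1 says: "A total of 20 healthy, postmenopausal female participants (N = 10 per arm) are planned for inclusion in this study". The justification is verbal ("The sample sizes provided are deemed sufficient to allow for adequate assessment of the IVR"), with no effect size, SD, alpha or power. Section 9.3 says: "Participants will be randomized in a 1:1 ratio to the two treatment groups"; it mentions no stratification. Section 9 defers the methods: "All statistical analyses will be described in a separate statistical analysis plan". The combined document, as available, holds no such SAP text.

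Table 1-1 schedules vital signs at Screening, at Cycle 1 Day 1 and at 12 later visits: Days 8, 15 and 22 of each cycle, Day 1 of Cycles 2 and 3, and Day 29. Section 7.7.2 defines baseline as the last measurement before first administration, but only for laboratory tests.

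**The concern.** The quantity named for comparison is the change score. If it is compared as it stands, two things follow when baseline and follow-up are imperfectly correlated.

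- The arm that starts higher by chance is expected to fall more, so a baseline imbalance enters the arm difference with the opposite sign.
- At low to moderate correlation the interval is wider than one that uses the baseline value as a covariate.

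Every visit's change subtracts the same baseline. One chance imbalance in, say, systolic pressure therefore pushes all 12 post-baseline contrasts for that measure the same way. A reader could take this for a sustained dose effect on a primary safety endpoint. The trial has no control group, so dose against dose is its only randomised contrast.

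**Working it through.** The plan gives no figure for this comparison, so there is nothing to reproduce.

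**Inputs.** n = 10 per arm and N = 20 (Section 9.1); 1:1 allocation (Section 9.3). The correlation ρ between baseline and follow-up is not in the protocol and is assumed over 0.3 to 0.9. Units are between-woman SDs. Equal SD at baseline and follow-up, normal data and no dropout are assumed.

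**Chance imbalance.** The baseline mean difference d has SD √(2/10) = 0.447. Its 95% range is ±1.96 × 0.447 = ±0.88. P(|d| > 0.5) = 2[1 − Φ(0.5/0.447)] = 0.264, or about 26%.

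**Shift in the raw-change difference given d, with no dose effect.** This is −(1 − ρ)d. For d = 0.5 the size is 0.7 × 0.5 = 0.35 at ρ = 0.3, 0.5 × 0.5 = 0.25 at ρ = 0.5, 0.3 × 0.5 = 0.15 at ρ = 0.7 and 0.1 × 0.5 = 0.05 at ρ = 0.9.

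**Precision.**
- Raw change: Var = (2/n) × 2(1 − ρ), with t on 18 df (2.101).
- ANCOVA: Var = (2/n)(1 − ρ²) × [1 + 1/(N − 4)], with t on 17 df (2.110). The last factor is 1.0625 and is the average cost of estimating the slope.
- Ratio, ANCOVA to raw change: 1.0625 × (1 + ρ)/2.

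| ρ | Variance ratio | 95% half-width, raw | 95% half-width, ANCOVA | Change in width |
|---|---|---|---|---|
| 0.3 | 0.69 | 1.112 | 0.928 | 16.5% narrower |
| 0.5 | 0.80 | 0.940 | 0.842 | 10.4% narrower |
| 0.7 | 0.90 | 0.728 | 0.695 | 4.5% narrower |
| 0.8 | 0.96 | 0.594 | 0.584 | under 2% narrower |
| 0.9 | 1.01 | 0.420 | 0.424 | 1% wider |

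The variance gain ends at ρ = 2/1.0625 − 1 = 0.88, and the gain in interval width at about 0.87.

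**Error rates.** These come from 100,000 simulated trials per ρ with no dose effect and a nominal 5% test.
- Over all randomisations, both analyses reject in 4.9 to 5.1% of trials.
- Among trials with |d| > 0.5, raw change rejects in 10.9%, 9.7%, 7.8% and 6.0% at ρ = 0.3, 0.5, 0.7 and 0.9. ANCOVA rejects in 4.8 to 4.9%.

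**The case against.** The strongest reply is that the protocol never says the comparison will be unadjusted. ANCOVA on the change with baseline as covariate is also a comparison of changes, so it fits the sentence in Section 9.6, and Section 9 leaves methods to a separate SAP. This stands. A reader might infer that the sponsor has chosen raw change scores, but the text is silent and supports only the statement that no adjustment is named.

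Second, the comparison carries little formal weight. It sits among descriptive summaries, with no hypothesis, alpha or decision rule. This also stands and limits the consequence. It does not remove it, because Section 9.6 promises a comparison on top of the summaries.

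Third, the raw change is not a biased analysis. Over all randomisations it is unbiased and keeps 5%, and its interval already allows for chance imbalance. The problem is conditional on the imbalance that the trial happens to draw.

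Fourth, a stronger precision claim is tempting. The large-sample ratio (1 + ρ)/2 is 0.75 at ρ = 0.5 and 0.85 at 0.7, which would equal 33% and 18% more women. With 20 women the ratios are 0.797 and 0.903, worth 1/0.797 = 1.25 and 1/0.903 = 1.11, so about 25% and 11%. A general claim of wasted precision fails at high correlation.

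Fifth, one might extend the point to vaginal pH, maturation index and MENQOL. Section 9.4.2 lists only changes such as "Mean change from baseline to Week 12 in vaginal pH" and plans no contrast between doses, so the extension has no basis.

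**Conclusion.** The point holds in a limited form. A between-arm comparison of vital-sign change is planned for a primary safety endpoint, no baseline adjustment is named, and baseline for vital signs is not defined. Baseline adjustment is the better estimate here, mainly because it removes the effect of an imbalance above 0.5 SD, which about one trial in four of this size will have for any given measure. The gain in precision is secondary: useful at correlations of 0.3 to 0.5, small at 0.7, almost nil at 0.8 and negligibly negative at 0.9.

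The 26% rests on the planned 10 per arm and approximate normality. The shifts and variance ratios also rest on equal SDs and on correlations that the protocol does not give and that may differ by measure and visit. The documents do not support saying that the sponsor will ignore baseline, or that the overall error rate is inflated.

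**What to change.** State in the SAP that:

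- any between-arm difference in vital-sign change is estimated by ANCOVA with the participant's own baseline value as covariate, at end of treatment and at each visit;
- it is reported as an adjusted difference with a 95% CI, for descriptive use;
- baseline for vital signs is the last measurement before insertion of the first IVR, matching the laboratory definition in Section 7.7.2;
- the unadjusted summaries by time point and arm are kept.

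A repeated-measures model is not needed. With 12 post-baseline visits an unstructured covariance has 12 × 13/2 = 78 parameters, which is hard to defend in 20 women.

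The cost is a few lines of SAP text and one degree of freedom per contrast. The schedule already collects vital signs at Screening and Cycle 1 Day 1, so no visit or measurement is added.
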